**Baseline medication:**

Baseline medication is defined as any medication with start date on or before study day 1 and ongoing while on study.

**Concomitant medication:**

Concomitant medication is defined as any medication with start date prior to study day 1 and ongoing while on study or any medication with start date on or after study day 1 and up to the EOS.

**Prior medication:**

Prior medication is defined as any medication with an end date prior to study day 1.

**UC related protocol-prohibited medications:**

**Following medications will be classified as UC related protocol-prohibited medications:**

Drug Class	Medication Restrictions
Anti-TNF antibodies (eg, infliximab, adalimumab, golimumab)	Discontinue at least 8 weeks prior to screening endoscopy and prohibited unless the subject has stopped investigational product permanently
Anti-integrin antibodies (eg, vedolizumab)	Discontinue at least 8 weeks prior to screening endoscopy and prohibited unless the subject has stopped investigational product permanently
IL-12/23 antagonist (eg, ustekinumab)	Discontinue at least 8 weeks prior to screening endoscopy and prohibited unless the subject has stopped investigational product permanently

JAK inhibitors (eg, tofacitinib)	Discontinue at least 4 weeks prior to screening endoscopy and prohibited unless the subject has stopped investigational product permanently
S1P modulators (eg, ozanimod)	Discontinue at least 4 weeks prior to screening endoscopy and prohibited unless the subject has stopped investigational product permanently
Any other commercially approved biologic agent or targeted small molecule	Discontinue at least 8 weeks prior to screening endoscopy or 5 half-lives prior to screening endoscopy, whichever is longer, and prohibited unless the subject has stopped investigational product permanently
Immunomodulatory medications oral cyclosporine, intravenous cyclosporine, tacrolimus, sirolimus, mycophenolate mofetil, or thalidomide	Discontinue at least 4 weeks prior to screening endoscopy and prohibited throughout duration of study
Any investigational biologic therapy	Discontinue at least 8 weeks prior to screening endoscopy or 5 half-lives prior to screening endoscopy, whichever is longer, and prohibited throughout duration of study
Apheresis (eg, Adacolumn® apheresis)	Discontinue at least 2 weeks prior to screening endoscopy and prohibited throughout duration of study
T cell depleting agents (eg, antithymocyte globulin, Campath).	Patients with exposure within 12 months prior to screening not eligible to be enrolled.
Recombinant IL-2 (eg, Proleukin®).	Patients with any previous exposure not eligible to be enrolled.
Corticosteroid enemas, corticosteroid suppositories, a course of IV	Discontinue at least 2 weeks prior to screening endoscopy and prohibited

corticosteroids or intramuscular corticosteroids, or oral budesonide standard formulation (not oral budesonide MMX)	unless the subject has stopped investigational product permanently
5-ASA enemas or 5-ASA suppositories	Discontinue at least 2 weeks prior to screening endoscopy and prohibited unless the subject has stopped investigational product permanently
Live vaccines	Last vaccination (if any) given at least 5 weeks prior to screening. Live vaccines are prohibited throughout the treatment period and for up to 6 weeks after the last dose of investigational product in the study.
Any other investigational therapies or device	Prohibited throughout duration of study.
Abbreviations: 5-ASA = 5-aminosalicylic acid; IL-2 = interleukin-2; IL-12/23 = interleukin 12/23; IV = intravenous; JAK = Janus Kinase; TNF = tumor necrosis factor; UC = ulcerative colitis.	

#### Concomitant UC medication:

Following medications will be classified as concomitant UC medication:

- **Oral 5-ASA**
- **Immunomodulators (azathioprine, 6-mercaptopurine, methotrexate)**
- **Oral corticosteroids**

#### Biologic Therapy Classes:

Biologic therapy classes include:

- Anti-TNF agents: **Infliximab, Adalimumab, Golimumab**
- Integrin receptor antagonists: **Vedolizumab**
- Interleukin inhibitors: **Ustekinumab (an anti-interleukin-12/23 antibody), Mirikizumab (a monoclonal antibody that targets the p19 subunit of interleukin-23), Risankizumab (a monoclonal antibody directed against the p19 subunit of IL-23)**

**Targeted Small Molecules:**

Targeted small molecules include:

- **Janus kinase (JAK) inhibitors: Tofacitinib and Upadacitinib**
- **Sphingosine-1-phosphate (S1P) receptor modulators: Ozanimod and Etrasimod**

**5.2 Study Points of Reference**

**Baseline:**

Baseline fecal calprotectin is the last measurement taken on or before the date of the first dose of IP.

Baseline for all other parameters is the last measurement for the endpoint of interest taken before the first dose of IP. If the measurement is taken on the same day as the first dose and the exact measurement time relative to the first dose is unknown, it will be assumed to have been taken prior to the first dose of IP.

If a subject did not receive IP, baseline is the closest recorded measurement on or prior to the randomization date for all parameters.

**Study Day 1:**

Study day 1 for each subject is the first day of IP administration or the day of randomization for subjects who did not receive IP.

**Study Day:**

Study day for each subject is defined as (day of interest - study day 1) + 1 for dates on or after study day 1, or (day of interest - study day 1) for dates prior to study day 1.

**5.3 Study Dates**

**End of Induction Date:**

End of Induction date for each subject is defined as date of the week 12 endoscopy. For subjects who discontinued from the study before completing the week 12 visit, or did not have a week 12 endoscopy, the end of induction date will be min(Study Day 90, EOS).

**Start of Long-Term Follow-Up treatment period:**

For subjects who continue into the long-term follow-up period, the start date is defined as the end of induction date plus one day.

**End of Study Date:**

EOS for each subject is the date recorded on the EOS eCRF page.

## 5.4 Arithmetic Calculations

### Change from Baseline:

The arithmetic difference between a post-baseline value and baseline for a given timepoint:

(post-baseline value – baseline value).

### Percent Change from Baseline:

The change from baseline divided by baseline value and multiplied by 100:

(change from baseline / baseline) \* 100.

If baseline is zero, the percent change from baseline will be set to zero.

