### Fold Change from Baseline:

Fold change from baseline equals the post-baseline value divided by the baseline value. If the change from baseline is not equal to 0 and the baseline value is 0 then fold change is not defined. If the change from baseline is equal to 0 and the baseline value is also 0 then fold change is 1.

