### **8.3 Handling of Missing and Incomplete Data**

Subjects may have missing specific data points for a variety of reasons. In general, data may be missing due to a subject's early withdrawal from study, a missed visit, or non-evaluability of a specific clinical measurement at its planned clinical visit. Missing data will not be imputed, except for the data points described below.

Non-responder imputation will be used to impute missing data for the following binary endpoints: clinical remission, clinical response, endoscopic remission, symptomatic remission, combined endoscopic and histologic remission, corticosteroid-free clinical remission.

If a subject has missing data for any of these endpoints, (including missing one or more subscores contributing to the endpoint) at any scheduled visit, the subject will be considered as not meeting the endpoint for that specific visit.

Missing data for the following continuous endpoints will be imputed with worst case imputation: change in Geboes score, total Mayo score, partial Mayo score, and individual Mayo subscores.

**Observed subscores will be used in the calculation of total and partial mayo score, where available. If one or more individual subscores is missing at a given post-baseline timepoint, the missing subscore will be imputed using the worst (highest) observed score across all available baseline and post-baseline visits up to week 12. The total/partial mayo score will be calculated using the imputed subscores, along with observed subscores, if available for that visit.**

Laboratory measurements that are below the lower quantification limits will be considered equal to the lower limit of quantification for all analyses unless explicitly noted otherwise.

Incomplete UC diagnosis date will be imputed as follows:

- If day is missing but month and year are present, impute to the last day of the month
- If day and month are missing and year is present, impute to the 31st December of that year

Missing and incomplete dates of medical history, procedures, AE, concomitant medication and hospitalization dates will be imputed as outlined in [Appendix C](#).

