#### **9.6.2            Laboratory Test Results**

Change and percent change from baseline in select clinical laboratory test results will be summarized over time by each treatment group. In addition, shift tables, from baseline to the worst on-study laboratory toxicity based on the CTCAE version 5 or later will be presented.

Subject incidence of worst post-baseline of eosinophils counts and percentages by the laboratory normal range will be tabulated by treatment group.

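### In the percent-change laboratory summaries, any rise from an exact-zero baseline is recorded as 0%, which is inconsistent with the SAP's own fold-change rule

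*SAP*

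**What the plan says.** SAP 5.4 (Arithmetic Calculations) gives three derivations one after another.

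- Absolute change is "The arithmetic difference between a post-baseline value and baseline for a given timepoint". It has no exception for a zero baseline.
- Percent change is "The change from baseline divided by baseline value and multiplied by 100", followed by: "If baseline is zero, the percent change from baseline will be set to zero".
- Fold change is the later value over the baseline value, with this condition: "If the change from baseline is not equal to 0 and the baseline value is 0 then fold change is not defined". It is 1 when both values are 0.

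SAP 9.6.2 puts percent change to use: "Change and percent change from baseline in select clinical laboratory test results will be summarized over time by each treatment group". The same section plans two outputs that do not use percent change: "shift tables, from baseline to the worst on-study laboratory toxicity based on the CTCAE version 5 or later will be presented", and "Subject incidence of worst post-baseline of eosinophils counts and percentages by the laboratory normal range will be tabulated by treatment group".

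SAP 8.3 also bears on when a baseline can be 0: "Laboratory measurements that are below the lower quantification limits will be considered equal to the lower limit of quantification for all analyses unless explicitly noted".

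**The concern.** Dividing by a zero baseline gives no defined percentage unless the later value is also 0, and even then 0% is a convention. Assigning 0% in every case states that nothing changed when something did. Because a count cannot fall below zero, a subject who starts at 0 and changes can only have risen, so the assigned value always understates that subject's movement.

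The assigned values then enter the statistics listed in SAP 9.1: mean, SD, median, quartiles, minimum, maximum and number of subjects with observations. Nothing in the table would show which values were calculated and which were set by rule.

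Protocol Appendix 2 (Table 11-1) lists eosinophils, basophils and bands in the hematology differential, where a reported 0 is plausible. Protocol 2.3 names changes in leukocyte population as a potential risk of the product. At stake is a diluted percent-change figure for low-count cell types, printed next to an absolute change that does show the rise.

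**Working it through.** **Inputs from the documents.** The three derivations in SAP 5.4; the summaries planned in SAP 9.1 and 9.6.2; the quantification-limit rule in SAP 8.3; 60 subjects per group (Protocol 4.1.1, SAP 3.1). The plan gives no figure to reproduce here, because the point concerns a derivation rule.

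**Step 1: apply the rules to single subjects.** The values are illustrative, not trial data.

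| Baseline | Later value | Change | Percent change (SAP rule) | Fold change (SAP rule) |
|---|---|---|---|---|
| 0 | 0 | 0 | 0% | 1 |
| 0 | 0.1 | 0.1 | 0% | not defined |
| 0 | 0.5 | 0.5 | 0% | not defined |
| 0 | 2.0 | 2.0 | 0% | not defined |
| 0.1 | 0.5 | 0.4 | 400% | 5 |

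The first four rows share one percent change, although only the first is a case of no change. Fold change separates them.

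**Step 2: effect on a group mean.** Let *f* be the share of subjects with a baseline of exactly 0. Assume that all of them rise and that every other subject doubles (+100%). Under the SAP rule the mean is *f* × 0 + (1 − *f*) × 100%. For 60 subjects:

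| *f* (assumed) | Zero baselines | Mean under SAP rule | Mean where defined | N where defined |
|---|---|---|---|---|
| 5% | 3 | 57 × 100 / 60 = 95% | 100% | 57 |
| 10% | 6 | 54 × 100 / 60 = 90% | 100% | 54 |
| 20% | 12 | 48 × 100 / 60 = 80% | 100% | 48 |
| 30% | 18 | 42 × 100 / 60 = 70% | 100% | 42 |

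The factor (1 − *f*) does not depend on the size of the rise. If the others rise by 200%, the means at 5%, 10% and 20% are 190%, 180% and 160%. The 100% column is the mean among subjects whose percent change exists. It is not a true value for the whole group, since the others have none.

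**Step 3: other statistics in this illustration.** The minimum becomes 0%. The first quartile becomes 0% once more than a quarter of the group has a zero baseline (18 of 60 at *f* = 30%). The median does not move until half the group has one. N is 60 under the SAP rule throughout.

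**Step 4: where the rule reaches.**

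- Laboratory percent change (SAP 9.6.2): affected, for any selected test with results reported as exactly 0.
- Laboratory absolute change, CTCAE shift tables and worst post-baseline eosinophils: not affected.
- Vital signs, weight and BMI (SAP 9.6.3, 9.6.4): percent change is planned, but a zero baseline is not plausible.
- Efficacy: the 30% reduction in clinical response is taken on the modified Mayo score, which is 5 to 9 at entry (Protocol 5.1, criterion 104), so its denominator is not 0.

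**The case against.** The strongest reply is that the consequence is slight, and most of that reply stands.

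- **The rise is visible elsewhere.** A reader might infer that a rise from zero is reported as no change across the laboratory safety summaries. The documents do not support that: SAP 9.6.2 summarizes absolute change alongside percent change, so a move from 0 to 0.5 enters that summary as +0.5.
- **No safety signal is shown to be hidden.** A reader might also link the rule to the eosinophilic drug reactions and leukocyte changes named as possible events of interest in SAP 9.6.1. Those are incidence summaries built from coded adverse-event queries, not from laboratory percent change. Eosinophils also have their own worst-value table. That table does not extend to basophils or bands, but absolute change and the shift tables do not use the rule either.
- **The reach is narrow and partly unknown.** SAP 9.6.2 covers only selected tests and does not list them. Under SAP 8.3 a result below the quantification limit is set to that limit, so the rule applies only where the laboratory reports a literal 0.
- **The fold-change contrast is between definitions, not outputs.** SAP section 10 marks biomarker analyses as not applicable, and no remaining analysis in this SAP is stated to use fold change.
- **Setting the value to missing does not show the rise either.** Absolute change does that under both rules.

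None of this makes 0% a correct value. Sound tables nearby do not justify an assigned number that cannot be told from a calculated one, and the SAP already contains the better logic.

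**Conclusion.** The point holds in a limited form. In the percent-change laboratory summaries only, SAP 5.4 assigns 0% to any rise from an exact-zero baseline. This pulls the mean toward no change, adds assigned values to N, and is inconsistent with the fold-change rule beside it.

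On assumed shares of 5% to 30% zero baselines, with those subjects rising and the others doubling, the reported mean is 95% down to 70%, against 100% among subjects with a defined value. Both the share and the doubling are assumptions. If no selected test has results reported as exactly 0, the effect is nil.

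Safety is summarized descriptively (SAP 9.1), and no efficacy endpoint or stated safety decision depends on the rule. Severity is minor.

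**What to change.** Replace the zero-baseline sentence under percent change in SAP 5.4 with a conditional one: when baseline is 0 and the later value is not 0, percent change is missing; when both are 0, it is 0%. This mirrors the fold-change logic already in that section. Footnote each affected percent-change table with the number of subjects excluded for this reason. Absolute change needs no edit, because it is already planned and keeps these subjects.

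The cost is one SAP sentence, one line of derivation code and a footnote, with no new data. The small downside is a lower N for that statistic (57 down to 42 of 60 in the illustration), which the footnote explains.

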### Fold Change from Baseline:

Fold change from baseline equals the post-baseline value divided by the baseline value. If the change from baseline is not equal to 0 and the baseline value is 0 then fold change is not defined. If the change from baseline is equal to 0 and the baseline value is also 0 then fold change is 1.

## 5.5 Definition of Study Endpoints

### Individual Mayo Subscore:

There are 4 Individual Mayo subscores; stool frequency, rectal bleeding, centrally read endoscopy findings, and physician's global assessment (PGA), with each subscore graded semi-quantitatively on a score of 0 to 3.

Further explanation given in [Appendix D](#) for the full definition of Mayo subscores and calculation.

### Total Mayo Score:

The total Mayo score is a composite index of the sum of the individual Mayo subscores, with each item graded semi-quantitatively on a score of 0 to 3, for a maximal total score of 12. The total Mayo score ranges from 0 to 12 points.

### Modified Mayo Score:

The modified Mayo score is the total Mayo score without the physician's global assessment subscore and ranges from 0 to 9 points.

### Partial Mayo Score:

The partial Mayo score is the total Mayo score without the endoscopy subscore and ranges from 0 to 9 points.

### Clinical Remission:

Clinical remission is defined as modified Mayo score 0 to 2 including rectal bleeding subscore of 0, a stool frequency subscore of 0 or 1, and a centrally read endoscopy subscore of 0 or 1 (modified so that 1 does not include friability).

### Clinical Remission (Using Local Endoscopy Score):

**Clinical remission is defined as modified Mayo score (based on local endoscopy score) 0 to 2 including rectal bleeding subscore of 0, a stool frequency subscore of 0 or 1, and a locally read endoscopy subscore of 0 or 1 (modified so that 1 does not include friability).**

### Clinical Response:

Clinical response is defined as a decrease from baseline in the modified Mayo score of  $\geq 2$  points and at least 30% reduction from baseline, and a decrease in the rectal bleeding subscore of  $\geq 1$  or an absolute rectal bleeding subscore of 0 or 1.

**Clinical Response (Using Local Endoscopy Score):**

**Clinical response is defined as a decrease from baseline in the modified Mayo score (based on local endoscopy score) of  $\geq 2$  points and at least 30% reduction from baseline, and a decrease in the rectal bleeding subscore of  $\geq 1$  or an absolute rectal bleeding subscore of 0 or 1.**

**Endoscopic Remission:**

Endoscopic remission is defined as Mayo centrally read endoscopy subscore of 0 or 1 (modified so that a score of 1 does not include friability).

**Endoscopic Remission (Using Local Endoscopy Score):**

**Endoscopic remission is defined as Mayo locally read endoscopy subscore of 0 or 1 (modified so that a score of 1 does not include friability).**

**Symptomatic Remission:**

Symptomatic remission is defined as Mayo stool frequency subscore of 0 or 1 and rectal bleeding subscore of 0.

**Combined endoscopic and histologic remission:**

Combined endoscopic and histologic remission is defined as combined endoscopic remission (Mayo centrally read endoscopy subscore of 0 or 1) and histologic remission of the colon tissue (Geboes Score  $< 2.0$ ; no neutrophils in the epithelium crypts or lamina propria and no increase in eosinophils, no crypt destruction and no erosions, ulcerations or granulation tissue [[Geboes, 2000](#)]).

**Rectal Bleeding and Stool Frequency Subscores:**

Rectal bleeding and number of stools per day will be recorded in the Mayo Daily Symptom Diary by the patient. The stool frequency subscore will be calculated based on the number of stools per day more than the reference number of stools. The reference number of stools is defined as the number of stools in a 24-hour period when in remission from UC prior to enrollment into the study. If the subject has never achieved remission, the number of stools per day before initial onset of signs and symptoms of UC will be used.

The subscores will be derived from the most recent 3 days of data entered within the last 7 days prior to the visit, or within 7 days prior to initiation of bowel preparations for visits which include an endoscopy.

Rules for consideration of visit dates are defined in [Appendix E](#).

**UC Complications:**

UC complications are defined as adverse events which have been categorized as related to UC on the Events eCRF.

**Worst Case Imputation:**

Worst case imputation will be used for missing postbaseline values for Geboes score, total Mayo score, partial Mayo score, and individual Mayo subscores. **In other words**, missing postbaseline values at any visit will be imputed using the highest score observed across baseline and all postbaseline visits.

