6.1.1.2 Dose Administration and Schedule in the Long-term Treatment Period

Subjects will continue to receive their assigned blinded dose of investigational product (placebo or efavaleukin alfa) beginning at the week 12 visit. The exception will be placebo nonresponder subjects, who are defined as those randomized to placebo during the induction period and failed to achieve clinical response at week 12. These placebo nonresponder subjects will be assigned in a blinded manner to receive [REDACTED] µg [REDACTED] dose during the long-term treatment period (Table 6-1). For the purposes of treatment assignment into the long-term treatment period, clinical response is defined as a decrease from baseline in the modified Mayo score (using the endoscopic subscore assigned by the investigator) of ≥ 2 points and at least 30% reduction from baseline, and a decrease in the rectal bleeding subscore of ≥ 1 or an absolute rectal bleeding subscore of 0 or 1.

Table 6-1. Investigational Product Administration: Long-term Treatment Period

Investigational Product Administration	
Induction Period	Long-term treatment period

Day 1 to Week 12	Week 12 up to Week 52 or Early Termination
Placebo [redacted] responder ^{a, d}	Placebo [redacted]
Placebo [redacted] nonresponder ^{b, d}	[redacted] µg [redacted]
[redacted] µg [redacted] d	[redacted] µg [redacted]
[redacted] µg [redacted] d	[redacted] µg [redacted]
[redacted] µg [redacted] d	[redacted] µg [redacted]

^a A placebo responder subject is one who achieved clinical response at week 12.

^b A placebo nonresponder subject is one who did not achieve clinical response at week 12.

^c Subjects randomized to efavaleukin alfa will remain on the same dose through the long-term treatment period and includes responders and nonresponders.

^d Clinical response for the purpose of treatment assignment in the exploratory long-term treatment period will be assessed using the modified Mayo score and the endoscopic subscore assigned by the investigator.

Subjects who were nonresponders at week 12, and who have an inadequate response by week [redacted] will be discontinued from further investigational product administration in long-term treatment period (Section 4.1.2).

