#### **9.5.3 Analyses of Secondary Efficacy Endpoint(s)**

The logistic regression model described in [Section 9.5.1.1](#) will be used to test the difference in rates between each efavaleukin alfa dose and placebo for the following secondary endpoints:

- Clinical response at week 12
- Endoscopic remission at week 12
- Symptomatic remission at week 12
- Combined endoscopic and histologic remission of the colon tissue at week 12

Subjects with missing data will be imputed using nonresponder imputation. The same incurrent event composite variable strategy as used for the primary estimand will be used for these secondary endpoints.

Change from baseline in histological score at week 12 as measured by Geboes score will be analyzed using an analysis of covariance (ANCOVA) model described in [Section 9.5.1.2](#). Subjects with missing week 12 Geboes score, or who experience any of the intercurrent events described in [Section 9.5.2](#) will be imputed using worst case imputation.

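### The worst-case rule for the week 12 Geboes score has no upper time limit, so a biopsy taken after induction can set a week 12 value; the likely effect is small.

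*SAP*

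**What the plan says.** Change from baseline in Geboes score at week 12 is a secondary endpoint, analyzed by ANCOVA (SAP 2.1 and Table 9-2).

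- **SAP 5.5, Worst Case Imputation**, lists Geboes, total Mayo, partial Mayo and the individual Mayo subscores. For all of them "missing postbaseline values at any visit will be imputed using the highest score observed across baseline and all postbaseline visits".
- **SAP 9.5.3** says who receives the rule: "Subjects with missing week 12 Geboes score, or who experience any of the intercurrent events described in" SAP 9.5.2 "will be imputed using worst case imputation". An observed week 12 score is therefore replaced too if the subject had an intercurrent event.
- **SAP 8.3** repeats the instruction without a cut-off: "Missing data for the following continuous endpoints will be imputed with worst case imputation: change in Geboes score, total Mayo score, partial Mayo score", and then the individual Mayo subscores. The paragraph after that opens with "Observed subscores will be used in the calculation of total and partial mayo score, where available" and says that "the missing subscore will be imputed using the worst (highest) observed score across all available baseline and post-baseline visits up to week 12". This is the only time limit on the rule.
- **SAP 5.3** puts the end of induction at the week 12 endoscopy. Without one, it is the earlier of study day 90 and end of study.
- **SAP Appendix B** gives Geboes two analysis windows: day 2 to the end of induction date, and the following day to day 378.
- **Protocol 4.1.1** asks subjects who stop product in induction to stay for assessments through week 52.

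**The concern.** An endpoint labelled week 12 should rest on data up to week 12. Under SAP 5.5, an imputed subject's value depends partly on whether a later biopsy exists and what it showed. Whether it exists depends on retention. What it shows may reflect other treatment, because Protocol 6.1.6 lifts the ban on biologics and targeted small molecules once product is stopped permanently. A flare months after induction could then be recorded as the week 12 result.

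The two SAP sections also disagree. For Mayo subscores, 5.5 takes all postbaseline visits and 8.3 stops at week 12. For Geboes, only the unlimited version applies. Among the endpoints in SAP Tables 9-1 to 9-3, Geboes is the only one that section 9.5 expressly sends to worst-case imputation, so the limit is missing where it matters most.

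**Working it through.** The documents give no rate of missing or overridden Geboes scores, no Geboes standard deviation and no expected effect of this rule, so there is no plan figure to reproduce. The check has two parts: what the rule does to one subject, and how far it could move an arm mean.

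**Step 1: which biopsies can enter.** Protocol Tables 1-1 to 1-3 schedule biopsies at screening, week 12 and week 52 or early termination. In practice one later biopsy per subject can enter. An early termination biopsy on or before the end of induction date falls in the first Geboes window and is the week 12 observation, so it is not a later value. One taken after that date falls in the second window and can enter.

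**Step 2: the rule for one imputed subject.** Let B be baseline, W the week 12 score if observed, and L the later score if available. Terms that are not available drop out.

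- As written: imputed change = max(0, W − B, L − B).
- Stopped at the end of induction: imputed change = max(0, W − B).
- Difference = max(0, L − max(B, W)).

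Illustration in arbitrary units, with B = 10 throughout:

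- W missing, L = 14: as written +4; stopped 0.
- W missing, L = 6: 0 under both.
- Intercurrent event, W = 7, L = 14: as written +4; stopped 0.
- Intercurrent event, W = 12, L = 8: +2 under both.

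The later biopsy can only raise the value, and only when it exceeds both baseline and any observed week 12 score.

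**Step 3: effect on an arm mean.** Shift = q × f × e, where q is the share of the arm imputed, f the share of those with a later score exceeding B and any W, and e their mean excess. All three are assumptions: q = 0.05-0.20, f = 0.10-0.40, e = 0.5-2.0 points.

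- Low: 0.05 × 0.10 × 0.5 = 0.0025 points.
- High: 0.20 × 0.40 × 2.0 = 0.16 points.
- Subjects changed in an arm of 60 (Protocol 4.1.1): 60 × 0.05 × 0.10 = 0.3 to 60 × 0.20 × 0.40 = 4.8.

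**Step 4: a check that does not depend on the scale.** Suppose baseline and week 52 scores are normal with equal SD and correlation 0.3-0.5, mean improvement at week 52 is 0-1 SD, and every imputed subject has a later biopsy but no observed week 12 score. Simulation gives a mean imputed change of 0.084 SD (correlation 0.5, improvement 1 SD) to 0.473 SD (correlation 0.3, no improvement). With the same q, the arm mean moves by 0.05 × 0.084 = 0.004 SD to 0.20 × 0.473 = 0.095 SD. In this model 16-50% of later scores exceed baseline, a wider range than in step 3.

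**The case against.** The strongest reply is that this is a wording gap with little consequence. Geboes change is one secondary endpoint with nominal p-values (SAP 9.1), in a trial that met its futility criteria (SAP 11). Clinical remission and the four binary secondary endpoints use nonresponder imputation. That stands, and it limits the weight of the point.

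It could also be said that the SAP 8.3 limit was meant for everything. The text does not say so. The limit sits in a paragraph on total and partial Mayo scores and their subscores, while Geboes is listed earlier without one.

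A third reply is that an unlimited maximum is simply more conservative. It does give higher imputed scores, but only for subjects who happen to have a later biopsy, and with data from outside the period the endpoint describes.

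A reader might infer that placebo nonresponders moved to efavaleukin alfa routinely feed long-term data into the placebo arm's week 12 result. Protocol 6.1.1.2 does say "These placebo nonresponder subjects will be assigned in a blinded manner to receive" efavaleukin alfa. But Protocol 4.1.2 admits to the long-term period only subjects who completed the week 12 evaluations and are still on product, and starting an excluded treatment ends product under Protocol 6.2.2.1. A switched subject is imputed only if the week 12 biopsy was missing or unevaluable, or if an intercurrent event, such as a dose increase in permitted UC medication, left product running. The route exists but is narrow.

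**Conclusion.** The point holds as a specification error. As written, SAP 5.5 and 9.5.3 let a week 52 or post-induction early termination biopsy set a week 12 Geboes value, and 5.5 conflicts with 8.3 for Mayo subscores. The main affected group is subjects who stop product in induction, remain on study and have a later biopsy.

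The effect is probably small: about 0.0025-0.16 Geboes points on an arm mean. Because every shift is upward, the distortion of a treatment difference is at most the larger arm's shift, and equal shifts would cancel. The range rests wholly on the assumed shares and excess in step 3.

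Two stronger readings are not supported:

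- A reader might infer that the week 12 Geboes result will change between the primary and final locks. SAP 7.2 evaluates secondary objectives at the primary analysis and locks those data, and 7.3 describes the final analysis as covering long-term data. A change would need week 12 Geboes to be re-derived at the final lock, which the SAP does not plan. The defect does not depend on this: with a single lock, later biopsies can still enter.
- A reader might infer a known bias between arms. Follow-up is encouraged in the same way in every arm. Unequal availability of later biopsies is possible, but nothing in the documents shows it.

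**What to change.** In SAP 5.5 and 9.5.3, state that for week 12 endpoints, Geboes included, the imputed value is the highest score over baseline and postbaseline visits up to the end of induction date. SAP 5.3 already defines that date. This brings 5.5 into line with 8.3 and makes the value independent of any later biopsy.

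The cost is one phrase in each of the two sections and one date filter in the derivation. The downside should be stated: with no other biopsy scheduled between screening and week 12, a missing week 12 Geboes score will usually be imputed as no change from baseline, which is slightly less conservative than the rule as written. After an intercurrent event, an observed week 12 score above baseline would still count.
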